7.4.1.3 Sensitivity analyses

7.4.1.3.1 Missing Not At Random data mechanism

These sensitivity analyses require partitioning the analysis mITT population into groups, based on treatment group and available information about the reasons for missing values, before multiple imputation.

Control-based I: all dropouts grouped with placebo

In the first control-based sensitivity analysis, all monotone missing values will be imputed such as all dropouts and the placebo group form a subset with similar trajectories. A dataset, MONOREF_all, containing all the placebo group subjects and the treatment group subjects with missing data, will be imputed as shown in sample SAS code below. The complement of MONOREF_all will be the complete observation treated group data, so this could be concatenated with the 20 imputed datasets in DATIMP1.

Sample SAS Code

```
proc mi data= MONOREF_all nimpute=1 seed=333 out=DATIMP1;
by _IMPUTATION_;
class GENETIC_MUT;
var GENETIC_MUT BASE CHANGE8 CHANGE24 CHANGE48;
monotone regression (CHANGE8 CHANGE24 CHANGE48);
run;
```

Control-based II (informative-dropout): poor-outcome dropouts grouped with placebo

In the informative-dropout sensitivity analysis, some subjects are characterized as likely to have poor unobserved outcomes, for example if study withdrawal is due to clinical worsening. In this case, the datasets in MONODAT (monotone dataset) will be first split by treatment groups, either randomized to the experimental (TRTGRP) or reference/placebo (REF) condition, and then the poor-outcome dropouts will be shifted to the REF group, resulting in the datasets MONOTRT_minus and MONOREF_plus. The multiple imputation will be conducted separately for each subset as shown in the following sample code. The output datasets, DATIMP2T and DATIMP2R, will simply be concatenated before the analysis step.

```
proc MI data= MONOTRT_minus nimpute=1 seed=444 out=DATIMP2T;
by _IMPUTATION_;
class GENETIC_MUT;
var GENETIC_MUT BASE CHANGE8 CHANGE24 CHANGE48;
monotone regression (CHANGE8 CHANGE24 CHANGE48);
run;

proc MI data= MONOREF_plus nimpute=1 seed=555 out=DATIMP2R;
by _IMPUTATION_;
class GENETIC_MUT;
var GENETIC_MUT BASE CHANGE8 CHANGE24 CHANGE48;
monotone regression (CHANGE8 CHANGE24 CHANGE48);
run;
```

Control-based III: poor-outcome dropouts act like reference

In the third control-based sensitivity analysis, the MNAR statement will be used to allow poor-outcome subjects to follow the expected trajectory of a subject in the reference group (see sample code below). Since the treated subjects from MONOTRT_minus are treated similarly as in the informative-dropout scenario, the results here in DATIMP3R could be contatenated with DATAIMP2T for analysis.

```
proc MI data= MONOREF_plus nimpute=1 seed=666 out=DATIMP3R;
by _IMPUTATION_;
class GENETIC_MUT;
var GENETIC_MUT BASE CHANGE8 CHANGE24 CHANGE48;
monotone regression;
mnar model (CHANGE8 CHANGE24 CHANGE48) / modelobs=(TRTGRP="REF");
run;
```

For each scenario, every 20 analysis estimates will be combined in one final estimate.

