#### **8.6.2 Assessment of target (plaque) background (blood) ratio with PET/CT**

Patients will have two PET/CT scans with labelled glucose  $^{18}\text{F}$ -deoxyglucose at Baseline and Week 24 only at the sites appropriately equipped.

The baseline PET/CT scan can be done anytime during the screening period, before the randomization.

All images will be collected for their review by an expert, with a window of +/- 7 days around the strict date.

The detailed procedure for performing and collecting PET/CT scans will be outlined in the Imaging Manual.

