### **12.2 Efficacy Assessments**

#### **12.2.1 Primary Efficacy Analysis**

The primary efficacy parameter of this study will be the change from baseline to 24 weeks in carotid MVWA in all randomised patients.

The primary efficacy endpoint, difference in the change from baseline in carotid artery Mean Vessel Wall Area (MVWA) at 24 weeks in patients treated with CER-001 compared to patients treated with placebo, will be analysed by an analysis of covariance (ANCOVA) model that includes treatment group and baseline MVWA as well as ABCA-1 or ApoA-1 genetic mutation as a covariate. Adjusted means for the change in MVWA in each treatment group and the difference between CER-01 and placebo will be provided, along with a 95% confidence interval.

Results (in terms of 95% confidence intervals for treatment effects) will also be presented for each of the ABCA-1 and ApoA-1 subgroups.

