## **12.5 Populations for Analysis**

The objectives of this study will be addressed primarily through the modified Intention-to-Treat (mITT) approach. In this approach all randomized patients with at least one valid, post randomization efficacy measurement, i.e., a follow up evaluation, will be included in the efficacy assessments, irrespective of their protocol adherence. Additionally, a per-protocol analysis will be performed which will only include patients who received all infusions of study drug (up to the time of each analysis), at the planned dosage and have no major protocol violations. Documentation of patients included / excluded from analysis populations will be completed before the study is unblinded.

For safety evaluations, all randomized patients who received at least one dose of study medication will be included.

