6.1 Analysis populations of patients

The statistical analysis will be based on the three populations defined below. To be part of a population, patients should have signed informed consent and fullfill all inclusion / exclusion criteria. Some criteria have been added after the start of the study. Hence patients included before will be considered as compliant to these criteria via a Not Applicable (NA) status.

Safety population

The safety population will comprise all randomized patients who received at least one dose of study medication.

Safety analysis will be performed on the safety population according to the actual treatment received.

Modified Intent-To-Treat (mITT) population

The mITT population will comprise all randomized patients for whom at least one of the following conditions is satisfied:

- 3T-MRI assessment available at baseline (W0) and at least one post-baseline 3T-MRI assessment available
- 18FDG-PET/CT assessment available at baseline (W0) and at least one post-baseline 18FDG-PET/CT assessment available

Per Protocol (PP) population

The PP population will comprise all patients of the mITT population without any major protocol deviations (*Cf.* section 6.3).

Defining study populations and excluding patients from the analysis will be a joint decision taken by Sponsor and ICTA PM' representatives (Statistician and Project Leader). Patients to be excluded and

CER-001-CLIN-009 CER-001

reasons for their exclusion will be discussed during data review meetings, before database lock and unblinding.

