7.3.2 Treatment compliance

Treatment compliance will be assessed on the mITT population according to randomized treatment group. Compliance (%) with the study treatment will be summarized on each study period (Induction / Maintenance / Extension) and at W24, W48 as follows:

- Compliance during induction phase (%) = Number of infusions totally administered between W0 and W8 / 9 * 100
- Compliance during maintenance phase (%) = Number of infusions totally administered between W10 and W24 / 8* 100
- Compliance during extension phase(%) = Number of infusions totally administered between W26 and W48 / 12 * 100
- Compliance at W24 (%) = Number of infusions totally administered between W0 and W24 / 17
 * 100
- Compliance at W48 (%) = Number of infusions totally administered between W0 and W48 / 29* 100

Average dose, total dose of CER-001 as well as administered dose *vs* expected dose will be summarized at W8, W24, W48, and are defined as follows:

- Total dose at Wi (mg) = $\sum_{v=1}^{ni} CER001$ dose prescription for infusion $v\left(\frac{mg}{kg}\right)$ * Weight at infusion $v\left(kg\right)$ * Actual volume administered at infusion $v\left(mL\right)$ / 250, when n_i = number of infusions received between W0 and Wi
- Average dose at Wi (mg) = Total dose at Wi (mg) / number of infusions received between WO and Wi
- Administered dose vs expected dose at Wi (%) = Total dose at Wi (mg) / (8 * $\sum_{v=1}^{mi} Weight$ at infusion v) * 100, when m_i = number of infusions planned between W0 and Wi

In addition, a by-patient listing will be produced for each patient who verified for at least one visit:

- Dose prescription different from 8 mg/kg
- Time elapsed between study medication infusion preparation and study medication administration > 72h (48h for Canadian sites)
- Start infusion time stop infusion time > 65 min or < 55 min
- Total volume administered = No

For these patients, the listing will include, for all available visits:

- Patient ID, visit, treatment arm
- Dose prescription (mg/kg)
- Date and time of study medication infusion preparation
- Date of infusion, start and stop infusion time
- If not administered, reason
- If infusion duration different from 60 min, reason

CER-001-CLIN-009 CER-001

- Total volume administered (Yes/No)
- If No, volume administered (mL)

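### The dropout sensitivity analyses for carotid MVWA run on mITT, so they leave out randomised patients who have a baseline scan but no follow-up scan

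*SAP*

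**What the plan says.** SAP 7.4.1.3.1 introduces the missing-not-at-random analyses with "These sensitivity analyses require partitioning the analysis mITT population into groups". In Control-based I, "all monotone missing values will be imputed such as all dropouts and the placebo group form a subset with similar trajectories". Control-based II and III treat only poor-outcome dropouts this way. The main MMRM (7.4.1.1) and the supportive multiple imputation (7.4.1.2) are also on mITT.

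SAP 6.1 admits a randomised patient to mITT by either of two routes: "3T-MRI assessment available at baseline (W0) and at least one post-baseline 3T-MRI assessment available", or "18FDG-PET/CT assessment available at baseline (W0) and at least one post-baseline 18FDG-PET/CT assessment available". Protocol 12.5 is similar, taking "all randomized patients with at least one valid, post randomization efficacy measurement", and makes mITT the primary approach. Protocol 12.2.1 words the primary parameter as "change from baseline to 24 weeks in carotid MVWA in all randomised patients".

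Under Protocol 8.3 the first scheduled follow-up MRI is at week 8, and the only follow-up PET/CT is at week 24. Protocol 8.7 asks for an MRI soon after any stop of study drug before week 24.

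On adherence, SAP 7.3.2 states: "Treatment compliance will be assessed on the mITT population according to randomized treatment group". SAP 7.3.1 summarises duration of exposure on the safety population.

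**The concern.** A control-based analysis asks what happens to the treatment effect if those who left did no better than placebo. It can ask this only about patients in the dataset. Requiring a follow-up scan removes those who left before giving one, so the exclusion made by mITT is not tested by the analyses meant to test dropout.

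The exclusion could differ by arm. Protocol 5 reports that infusion reactions were more frequent on CER-001 than on placebo in earlier studies, and nine of the 29 infusions fall between week 0 and week 8. If early leavers with no scan were mainly on CER-001, the randomised comparison would be altered and every planned sensitivity analysis would be silent about it. The compliance and dose tables would lose the same patients, who have the fewest infusions.

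**Working it through.** **1. The plan's own figure.** Inputs from SAP 3: difference 6.7%, SD 4.5%, 16 and 8 completers, two-sided alpha 0.05.
- Standard error = 4.5 x sqrt(1/16 + 1/8) = 1.95; noncentrality = 6.7/1.95 = 3.44; 22 degrees of freedom.
- Two-sample t-test power = 90.7%, which agrees with the stated 90%.
- 24/(1 - 0.20) = 30 randomised, as stated. At 2:1 this is 20 CER-001 and 10 placebo, with an allowance of 30 x 0.20 = 6 discontinuations.

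**2. Who is left out.** Take a patient with a baseline MRI who leaves at week 3 and has no further scan.
- MRI route into mITT: no post-baseline MRI, so not met.
- PET/CT route: no week-24 PET/CT, so not met.
- Per protocol: a subset of mITT, so not met.
- Safety population: included, but SAP 7.4 uses it for no efficacy analysis.

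The patient is thus absent from the MMRM, the multiple imputation and all three control-based analyses.

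**3. Could the patient be imputed?** The Control-based I model uses mutation, baseline, CHANGE8, CHANGE24 and CHANGE48. Genotype is mandatory at screening, and the baseline MRI is planned before the first infusion. With all three changes missing the pattern is already monotone, so the stated code applies.

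**4. Size.** Assume 20 CER-001 patients, a 6.7% difference while on drug, and k CER-001 patients with no follow-up scan who behave like placebo. The all-randomised difference is

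[(20-k) x 6.7 + k x 0]/20 = 6.7 x (20-k)/20.

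| k | All randomised | mITT |
|---|---|---|
| 0 | 6.7% | 6.7% |
| 1 | 6.7 x 19/20 = 6.4% | 6.7% |
| 2 | 6.7 x 18/20 = 6.0% | 6.7% |
| 4 | 6.7 x 16/20 = 5.4% | 6.7% |
| 6 | 6.7 x 14/20 = 4.7% | 6.7% |

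k=4 is 20% of the CER-001 arm. k=6 puts the whole trial's allowance in that arm. The factor (20-k)/20 is the same for change in mm², the scale of the SAP model.

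**5. Chance of p<0.05.** This comes from a simplified simulation: one visit, no covariates, placebo change 0, SD 4.5, imputation from the placebo arm, 20 imputations, 1,500 runs.

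| Early leavers, CER-001 / placebo | All randomised | Left out |
|---|---|---|
| 1 / 0 | 94% | 95% |
| 2 / 0 | 90% | 95% |
| 4 / 0 | 78% | 94% |
| 4 / 2 | 70% | 91% |
| 6 / 0 | 56% | 92% |

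These figures are illustrative only.

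**6. Which analyses would move.** The shift in step 4 belongs to Control-based I, and to II and III for patients classed as poor-outcome. The imputation in 7.4.1.2 has treatment in its model, so added CER-001 patients would be imputed like other CER-001 patients and the expected difference would hardly change. Running it on the same set keeps the analyses comparable.

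**The case against.** The strongest reply is that the gap is narrow and partly managed. Protocol 8.7 requests an MRI after any stop before week 24, and Protocol 9.12 says that stopping drug is not withdrawal from the study. A patient who stops after an infusion reaction is therefore meant to be scanned and would enter mITT. Protocol 12.5 makes mITT primary, and the sample size is stated in mITT completers. SAP 6.3 reports numbers in each analysis set with reasons for exclusion, and SAP 7.3.1 shows exposure on the safety population, so the loss would be visible. The count k is unknown and may be zero.

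Most of this stands, and it limits the point to patients with no follow-up scan at all. It does not close the gap. Protocol 9.12 foresees patients who withdraw consent and refuse to return, for whom it plans at most a telephone contact. A disposition table counts such patients but does not show what they do to the estimate.

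Three stronger readings are tempting and are not supported:
- A reader might take Control-based I as a worst-case analysis. The SAP does not call it that, and the observed values of treated dropouts enter its imputation model. Its reference to all dropouts also sits in a section that names mITT at the outset.
- A reader might take Protocol 12.2.1 to make all randomised patients the only target. Protocol 12.5 says otherwise.
- A reader might think that the PET/CT route makes inclusion of early leavers depend on site equipment, since PET/CT is done "only at the sites appropriately equipped". That route needs a week-24 scan, so it does not bear on patients who leave early.

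**Conclusion.** The point holds in this limited form. Randomised patients with a baseline carotid MRI and no follow-up scan are outside every efficacy analysis, so the control-based analyses cannot test the effect of excluding them. The main MMRM on mITT follows Protocol 12.5 and is not in question.

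The size depends wholly on k, which the documents do not give. Each affected CER-001 patient of 20 lowers the all-randomised difference by 1/20, or 5% of its planned value: nothing at k=0, 6.4% at k=1, 5.4% at k=4. This assumes that such patients behave exactly like placebo and that the planned 6.7% holds for the rest. The figures do not predict bias in this trial. They show what the planned analyses could not reveal if early loss occurred. The change is worth making because it is cheap.

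The compliance point is smaller. Adherence and dose would be summarised without the patients who left before any scan, on a different set from exposure.

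**What to change.** Before unblinding, amend the SAP as follows.
- Keep mITT for the main MMRM in 7.4.1.1.
- Run the multiple imputation in 7.4.1.2 and the three control-based analyses in 7.4.1.3.1 on all randomised patients with a baseline carotid MRI, imputing CHANGE8, CHANGE24 and CHANGE48 where there is no follow-up MRI. Define this set in 6.1.
- Summarise compliance and dose in 7.3.2 on the safety population, as 7.3.1 does for exposure.

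The cost is SAP wording, one more defined analysis set, and the same code on a slightly larger dataset. A few patients would have all three changes imputed from baseline and mutation alone, with a reference group of about 10 placebo patients plus treated dropouts. The sensitivity estimates may therefore be wider and less favourable; with several such patients the loss could be appreciable, as step 5 of the working shows. If there are none, the MVWA sensitivity results do not change on their account.

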7.4.1.3.2 Analysis on the PP population

Primary efficacy analysis described for ITT population will also be performed on PP population in the same way (see sections 7.4.1.1 & 7.4.1.2).

7.4.2 Secondary endpoints

All secondary endpoints will be analysed on the mITT population.

CER-001-CLIN-009 CER-001

7.4.2.1 Change from baseline in carotid artery MVWA

Estimators of the secondary endpoints listed below will be obtained using the mixed model already fitted in section 7.4.1.1:

- Difference in change (Experimental treatment vs placebo) from baseline (W0) in carotid artery
 MVWA at 8 weeks
- Difference in change (Experimental treatment vs placebo) from baseline (W0) in carotid artery MVWA at 48 weeks

7.4.2.2 Change from baseline in femoral artery MVWA

A linear mixed model with repeated measures (MMRM) will be fitted to observed data for the mITT population without any imputation. An unstructured covariance matrix will be used to model random effects. The model will include the following variables:

- Change from baseline in femoral artery MVWA (mm², dependent variable)
- Randomized treatment group (CER-001 vs Placebo, independent variable)
- Genetic mutation (ABCA-1/ApoA-1/ABCA-1 and ApoA-1), independent variable)
- Femoral artery MVWA at W0 (mm², covariate)
- Visit (W8/W24/W48, independent variable)
- Treatment-by-Visit interaction (independent variable)
- Femoral artery MVWA at W0 by Visit interaction (independent variable)
- Treatment-by-femoral artery MVWA at W0 (independent variable)
- Subject (random factor)

Analysis will be based on that described for the main analysis of the primary endpoint (section 7.4.1.1). No multiple imputation will be performed.

The following differences between placebo and the experimental treatment will be estimated:

- Change from baseline (W0) in femoral artery MVWA at 8 weeks
- Change from baseline (W0) in femoral artery MVWA at 24 weeks
- Change from baseline (W0) in femoral artery MVWA at 48 weeks.

These estimators will also be calculated within each genetic mutation.

7.4.2.3 Change from baseline in target (plaque) to background (blood) ratio

An analysis of covariance (ANCOVA) will be fitted to observed data for the mITT population without any imputation. The model will include the following variables:

- Change from baseline (W0) in TBR based on standardized 18FDG uptake measured with 18FDG-PET/CT MVWA at 24 weeks (dependent variable)
- Randomized treatment group (CER-001 vs Placebo, independent variable)
- Genetic mutation (ABCA-1/ApoA-1/ABCA-1 and ApoA-1), independent variable)
- TBR at W0 (covariate)
- Interaction Treatment by TBR at W0 (independent variable)

Adjusted means for the change in TBR and the associated 95%CI will be provided for each randomized treatment group. Adjusted mean difference and the associated 95%CI will also be displayed.

CER-001-CLIN-009 CER-001

Sample SAS Code

```
proc glm data=DATWIDE alpha=0.05;
    class TRTGRP GENETIC_MUT;
    model CHANGE24 = BASELINE GENETIC_MUT BASELINE*TRTGRP TRTGRP / s;
    lsmeans TRTGRP / cl pdiff=control("REF");
run;
```

The previous statistics will also be estimated within each genetic mutation.

A scatter plot will be drawn representing the evolution of the TBR at week 24 according to the baseline TBR grouped by treatment group. Adjusted means (with 95%CI) for the change from baseline in each randomized treatment group will also be plotted.

7.4.3 Exploratory endpoints

The following exploratory endpoints will be summarized on the mITT population overall according to randomized study treatment and for each genetic subgroup within the randomized group using descriptive statistics:

- Percent change from baseline in femoral artery MVWA at 8, 24, 48, 72 weeks
- Percent change from baseline in maximum vessel wall thickness (MaxVWT) at 8, 24, 48, 72 weeks
- Percent change from baseline in mean vessel wall thickness at 8, 24, 48, 72 weeks
- Absolute and percent change in carotid mean vessel wall volume (MVWV) at 8, 24, 48, 72 weeks
- Percent change from baseline in the mean of the carotid normalized wall index at 8, 2448, 72 weeks
- Absolute and percent change from baseline in femoral artery MVWV at 8, 24, 48, 72 weeks

Percent change from baseline at Wi is defined as follows:

```
(Value at Wi – Value at baseline (W0)) / Value at baseline (W0)*100
```

Vessel wall biology (C-reactive protein (mg/L), PON-1 (IU/L), MMP-9, TNF α , IL-6, soluble VCAM-1, sMCP1, oxysterols, ABCA-1 mRNA and protein levels) will be summarized at screening, W0 (baseline), W4, W8, W24, W48. Absolute and relative changes from W0 (baseline) at W8, W24 and W48 will also be summarized. For changes calculation, if value at W0 is missing then value observed at screening will be used.

Cholesterol efflux capacity will be summarized at screening, W0, W8, W24 and W48. Absolute and relative changes from W0 (baseline) at W8, W24 and W48 will also be summarized. For changes calculation, if value at W0 is missing then value observed at screening will be used.

Lipid profile will be summarized at screening, W0, W8, W24 and W48. Absolute and relative changes from screening at W8, W24 and W48 will also be summarized (LABTYPE = Lipids):

- Total Cholesterol (mmol/L)
- Free Cholesterol (mmol/L)

CER-001-CLIN-009 CER-001

- Esterified Cholesterol (mmol/L)
- LDL Cholesterol (mmol/L)
- HDL Cholesterol (mmol/L)
- Triglycerides (mmol/L)
- Apolipoprotein A-1 (g/L)
- Apolipoprotein A-2 (g/L)
- Apolipoprotein B (g/L)
- Apolipoprotein C-3 (g/L)
- Apolipoprotein E (g/L)

For changes calculation, if value at W0 is missing then value observed at screening will be used.

HDL-C Particle Size (2D-gel/NMR) will be summarized at screening, W0, W8, W24 and W48. NMR laboratory tests are the following (LABTYPE = Liposcience):

HDL particles (μmol/L), Large HDL particles (μmol/L), Medium HDL particles (μmol/L), Small HDL particles (μmol/L), HDL size (nm), IDL particles (nmol/L), LDL particles (nmol/L), LDL particles (nmol/L), LDL size (nm), HDL cholesterol (mg/dL), Triglyceride (total) (mg/dL), VLDL & Chylomicron Triglyceride (total) (mg/dL), Large VLDL & Chylomicron Particles (nmol/L), VLDL & Chylomicron Particles (total) (nmol/L), Medium VLDL Particles (nmol/L), Small VLDL Particles (nmol/L), VLDL Size (nm).

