### EXPLORATORY EFFICACY PARAMETERS:

- Changes from Baseline in carotid normalized wall index assessed by 3T-MRI from baseline to week 24 and week 48.
- Changes from baseline to week 24 and week 48 of potential markers on vessel wall biology including and not restricted to laboratory variables such as absolute and relative change in high sensitivity C-reactive protein (hs-CRP), MMP-9 and other selected inflammatory markers (TNF $\alpha$ , IL-6), soluble VCAM-1, PON-1 and sMCP1, plaque characterization indexes using 3T-MRI.
- Cholesterol efflux capacity after CER-001 administration.
- Changes from baseline of ApoA-1 level.
- Changes from baseline in total cholesterol, unesterified cholesterol, esterified cholesterol, triglycerides, apolipoprotein B, other apolipoprotein and lipoprotein profiles for total and unesterified cholesterol by HPLC.

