**Clinical**

5. Diagnosis of genetically confirmed HDL-c deficiency due to defects in genes coding for e.g. ABCA1 and/or ApoA-1
6. IF the subject is on lipid-lowering therapy or NEEDS to be treated with lipid-lowering therapy then the subject must be on a stable dose at least 6 weeks prior to the baseline procedures.
7. Background symptomatic or asymptomatic cardiovascular disease should be present as such:
  - For symptomatic cardiovascular disease: i) history of cardio or cerebrovascular events, ii) diagnosed coronary artery disease (CAD), iii) diagnosed carotid or peripheral stenosis, iv) previous myocardial revascularisation - percutaneous coronary intervention (PCI), or coronary artery bypass graft (CABG).
  - For asymptomatic cardiovascular disease: patients with subclinical atherosclerosis diagnosed using imaging method such as i)vDoppler ultrasound, ii)vB-mode ultrasonography – measurement of carotid intima media thickness, iii)vintravascular ultrasonography, iv) Computed Tomography, v) Magnetic Resonance Imaging
8. ApoA-1  $\leq$  110 mg/dL
9. HDL-cholesterol  $\leq$  35 mg/dL or 0.9 mmol/L

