## **12 STATISTICS**

### **12.1 Statistical Methods**

Data will be analyzed by the mandated CRO. All cases will be checked for consistency and completeness by the Data Management Department of the mandated CRO.

Demographic and other baseline characteristics will be summarized across all randomized patients. Baseline is defined as the last observation for any given parameter prior to the first infusion of study drug. Comparability at baseline among treatment groups will be assessed using descriptive statistics without formal statistical tests.

The statistical techniques that are proposed in the sections below require certain assumptions. These assumptions will be checked for validity, and if they are not tenable, then appropriate statistical procedures will be utilized to complement the proposed procedures. Further detail on the statistical analysis is provided in the TANGO Statistical Analysis Plan (SAP) and decisions about analysis methods based on distribution assumptions will be documented in a review of the data before unblinding.

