7.1.9 Validation levels

Internal review by the statistician in charge of the project will be performed, including SAS® codes and programming, SAS® logs and outputs and edition of the TFL. Then, an external review of the TFL will be performed by the ICTA PM project manager and by the sponsor.

A double-programming of the primary endpoint analysis will be performed.

7.2 Demographic and other baseline characteristics

Demographic and other baseline characteristics will be described according to randomization group for all randomized patients. Description will also be performed for each subgroup of interest (based on genetic mutation). Baseline is defined as the last observation for any given parameter observed prior to the first infusion of study drug.

The following characteristics will be summarized using standard descriptive statistics (Cf. 7.1.2):

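### SAP 7.4.3 gives two conflicting reference points, screening and W0, for change in the lipid profile

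*SAP*

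**What the plan says.** SAP 7.4.3 deals with three groups of laboratory endpoints in turn: vessel wall biology, cholesterol efflux and the lipid profile. For the first two the rule is: "Absolute and relative changes from W0 (baseline) at W8, W24 and W48 will also be summarized". For the lipid profile, which includes ApoA-1, it is: "Absolute and relative changes from screening at W8, W24 and W48 will also be summarized". All three end with the same fallback: "For changes calculation, if value at W0 is missing then value observed at screening will be used".

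SAP 7.2 sets a general rule: "Baseline is defined as the last observation for any given parameter observed prior to the first infusion of study drug". Protocol 12.1 gives the same rule in almost the same words. The exploratory efficacy parameters in the protocol synopsis are expressed against baseline: "Changes from baseline of ApoA-1 level", and "Changes from baseline in total cholesterol, unesterified cholesterol, esterified cholesterol, triglycerides" among other lipid measures.

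The SAP introduction says that the SAP takes precedence over the protocol and that changes are reported in section 10. Section 10 reports only the move from ANCOVA to a mixed model for the primary and secondary outcomes.

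**The concern.** The lipid paragraph tells the programmer to subtract the screening value, then gives a fallback that assumes the W0 value is being subtracted. The two instructions give different numbers for every patient who has both samples and whose lipids moved in between.

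Such movement is plausible. Inclusion criterion 6 covers patients who need lipid-lowering therapy as well as those already on it, and requires only that "the subject must be on a stable dose at least 6 weeks prior to the baseline procedures". Advice on diet and lifestyle is given at the screening visit (protocol 8.1). A screening reference would report the effect of either as change at W8, W24 and W48. These tables carry the pharmacodynamic evidence, and they are also broken down by genetic subgroup within arm, where a few patients can move a mean.

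**Working it through.** The plan states no figure on this point to reproduce. The check is a comparison of text, followed by an illustration on assumed inputs.

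**1. Which reference each place uses**
- SAP 7.4.3, lipid profile, main sentence: screening.
- SAP 7.4.3, lipid profile, fallback: W0, or screening if W0 is missing.
- SAP 7.4.3, vessel wall biology and cholesterol efflux: W0, same fallback.
- SAP 7.1.4, safety laboratory values: W0, with screening if it is missing.
- SAP 7.2 and protocol 12.1: last value before the first infusion, for any parameter.
- Protocol synopsis, lipid and ApoA-1 endpoints: baseline.
- SAP section 10: no change of lipid reference declared.

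The lipid main sentence stands alone. A W0 sample is scheduled (protocol 8.9 and Appendix A), so lack of data does not explain it.

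**2. Whether the two lipid sentences can both hold**

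Let S be the screening value, B the W0 value and Y the value at a later visit.
- B missing: both rules give Y − S. They agree.
- B present: the main sentence gives Y − S, and the fallback implies Y − B. They differ by (Y − S) − (Y − B) = B − S.

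They therefore conflict for every patient with a W0 sample, by exactly the change between screening and W0. The relative change also switches its denominator from B to S. The fallback agrees with the general baseline rule, because when W0 is missing the screening value is the last one before infusion.

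**3. What can enter B − S**

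Screening lasts up to 16 weeks (protocol 6.1.1) and the stability requirement is 6 weeks (criterion 6). The nominal window for a therapy change after the screening sample is 16 − 6 = 10 weeks. This is an upper limit: it shrinks if screening is shorter or if baseline imaging, allowed at any time in screening (protocol 8.6), is done early.

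**4. Illustration for LDL-C (all inputs assumed)**

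Suppose a share f of patients changes therapy in that window, their LDL-C falls by a fraction q before W0, and nothing else changes. The mean change from screening is −f × q; from W0 it is 0%.
- f = 0.10, q = 0.20: −0.10 × 0.20 = −2%.
- f = 0.30, q = 0.40: −0.30 × 0.40 = −12%.

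In small groups a single patient matters. A 30% fall in one patient moves the mean by 30/10 = 3 percentage points in a placebo arm of 10, and by 30/3 = 10 points in an assumed subgroup of 3.

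**5. Effect on the comparison of arms**

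B − S arises before randomized treatment starts, so its expectation is the same in both arms and it creates no difference between them on average. Chance imbalance remains. With 30 patients randomized 2:1 (20 and 10), the SD of the difference in mean percent change from this source is q × √[f(1 − f)(1/20 + 1/10)].
- f = 0.10, q = 0.20: 0.20 × √(0.09 × 0.15) = 2.3 percentage points.
- f = 0.30, q = 0.40: 0.40 × √(0.21 × 0.15) = 7.1 percentage points.

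**The case against.** The strongest reply is that this is a one-word drafting slip. The fallback sits in the same block, the two preceding paragraphs follow the same template with W0, and the baseline definition covers any parameter. A careful programmer would probably use W0. That stands, and it rules out the stronger reading that the sponsor chose screening deliberately or that lipid changes will certainly be computed from it. The text still holds two instructions, and only the primary endpoint analysis is double-programmed (SAP 7.1.9).

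The consequences are also limited. The endpoints are exploratory and summarized without a test. Lipids are tabulated at both screening and W0 by arm, so drift before treatment can be seen, and the placebo column shows the same expected shift. Therapy changes during screening are permitted but not shown to occur. Nor does a W0 reference guard against changes of therapy after W0, since protocol 7.6 allows any medically necessary medication. All of this stands.

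A reader might also infer regression to the mean, because patients are selected on HDL-C, ApoA-1 and triglycerides. The documents do not support a claim of that kind. Criteria 8 and 9 do not say which sample decides eligibility. Protocol 8.9 withholds central lipid results until database lock, apart from screening triglycerides and any triglyceride value above 1000 mg/dL. The HDL-C and ApoA-1 values used for selection may therefore not be the screening values in the analysis. For triglycerides, selection on the screening sample is plausible, but no distribution or within-person variation is given from which to size an effect.

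**Conclusion.** The point holds as an inconsistency to be corrected, and it is minor. SAP 7.4.3 specifies two reference points for lipid change. The screening reference contradicts the plan's own baseline definition and the protocol endpoints, and it is not declared in section 10.

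If it is programmed literally, each patient's absolute change is off by the shift from screening to W0. The documents give no size for that shift. The range of −2% to −12% for LDL-C rests wholly on the assumed 10–30% of patients changing therapy and 20–40% lowering in those patients; it shows scale and is not an estimate.

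A reader might infer that the drug–placebo comparison is biased, or that the trial's main result is at risk. Neither follows. Changes before W0 are balanced between arms in expectation, and the primary MVWA analysis takes its baseline at W0.

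**What to change.** In the lipid paragraph of SAP 7.4.3, replace *changes from screening* with *changes from W0 (baseline)*, and leave the fallback as it stands, so that screening is used only when the W0 value is missing. If screening was in fact intended, state and justify it in section 10 and delete the fallback.

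The cost is one phrase before database lock. W0 lipid samples are already scheduled, and no new data, test or table is needed.
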